7. STUDY DESIGN

Study Center(s): Multicenter Transplant Alliance – Kidney Centers

Study Design: This is a prospective, multi-center, observational, open-label, study comparing transplant-specific patient reported outcomes and medication adherence between Envarsus XR® and immediate release tacrolimus medication in adult renal transplant recipients. The study will enroll 240 patients and survey these same 240 patients at three time points during the study.

Clinical Study Protocol [#SIMPLE]

Study Design Rationale:

Patients will be enrolled into the study within the first 30 days post-transplant. Treatment will not be determined by this study, and there is no intervention. The treatment decision will be made by each patient's transplant care team, independent of the study.

For the primary objective, comparison of calcineurin inhibitor related symptoms, a standard two-group design will be used to compare treatment groups. These groups will also be compared for transplant-related symptoms, health-related quality of life, adverse events, patient satisfaction, adherence, dnDSA, and graft function.

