10. DEVIATION FROM TREATMENT REGIMEN

If deviation occurs from treatment, patient will continue study. Patient reported outcome measures will be completed as scheduled and samples will be taken as scheduled. Reason(s) for deviation will be recorded.

Criteria for Study Termination

The investigator can discontinue the study participant at any time for any reason, including development of severe adverse events, uncontrolled infection, or other clinical/administrative reasons. Allograft loss and death will be cause for automatic withdrawal from the study. If a patient unable to continue the study for any reason, an early termination visit is necessary to complete the study. If the patient needs to be started on immunosuppression that is listed in the exclusion criteria of this study, an early termination visit is necessary to complete the study.

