14. TIMING OF VISITS

Visit 1: Baseline/Screening

To be collected within the first 30 days post-transplant

- Informed consent
- Demographics
- Medical history
- Complete physical exam including vital signs, height, and weight
- Determination of eligibility based on inclusion/exclusion criteria
- Hematology panel
- Electrolytes including creatinine and eGFR
- Urinalysis
- Baseline Surveys:
 - HRQoL: PROMIS -29 profile (29 questions) measuring depression, anxiety, fatigue, pain interference, sleep disturbance, physical function, participation in social roles, and pain intensity
 - PRO-CTCAE: Calcineurin-inhibitor related symptoms (5 items) and the Transplant related symptoms (14 items)
 - FACT – G (GP5): Single item bothersome assessment (1 question)
 - The PROMIS Self-Efficacy for Managing Medication and Treatment (26 questions) – (study visit 1 only).

Visit 2: Day 120 ± 30 days

All subjects will complete the following prior to morning tacrolimus administration:

- Vital signs, height, and weight
- Hematology panel
- Electrolytes including creatinine and eGFR Tacrolimus trough
- Surveys including:
 - HRQoL: PROMIS -29 profile (29 questions) measuring depression, anxiety, fatigue, pain interference, sleep disturbance, physical function, participation in social roles, and pain intensity
 - PRO-CTCAE: Calcineurin-inhibitor related symptoms (5 items) and the Transplant related symptoms (14 items)
 - FACT – G (GP5): Single item bothersome assessment (1 question)

Visit 3: Day 365 ± 45 days (end of study visit)

All subjects will complete the following prior to morning tacrolimus administration:

- Vital signs, height, and weight
- Hematology panel
- Electrolytes including creatinine and eGFR Tacrolimus trough
- Surveys including:

Clinical Study Protocol [#SIMPLE]

- HRQoL: PROMIS -29 profile (29 questions) measuring depression, anxiety, fatigue, pain interference, sleep disturbance, physical function, participation in social roles, and pain intensity
- PRO-CTCAE: Calcineurin-inhibitor related symptoms (5 items) and the Transplant related symptoms (14 items)
- FACT – G (GP5): Single item bothersome assessment (1 question)
- The Transplant Satisfaction Questionnaire for Medication – question 14.

SCHEDULE OF EVENTS

	Baseline (Within the first 30 days post- transplant)	4 Months Post- Transplant	12 Months Post- Transplant (End of Study)
STUDY VISIT NUMBER	1	2	3
Test/Procedures/Data Collection			
Informed Consent	X		
Review of Inclusion/Exclusion Criteria	X		

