For analyses of the CIRS, TRS, and PROMIS-29 scores, we will first calculate change within individuals from enrollment to 12 months. Analysis of covariance (ANCOVA) will be used to compare change between treatments, adjusted for baseline score. The ANCOVA model-estimated mean difference between treatments will be divided by the pooled baseline standard deviation to calculate effect size measures to aid in interpretation. Medication adherence and change in eGFR will be compared between groups using similar models.

For analyses of individual transplant-related symptoms and side effect bother (GP5), within-patient change on each item will be classified as improved, worsened or unchanged and compared between treatments using chi-square tests for ordinal data. Medication satisfaction responses at 12 months will be compared between treatments using an ordinal chi-square test.

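### Failed grafts have no defined value in the 12-month eGFR comparison, so by default it becomes a comparison of surviving grafts that can hide a difference in graft loss

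*Combined protocol and SAP*

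**What the plan says.** Graft function is a declared between-group comparison. Section 7 says: "These groups will also be compared for transplant-related symptoms, health-related quality of life, adverse events, patient satisfaction, adherence, dnDSA, and graft function". The Synopsis design rationale also names graft function.

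The only analysis stated for it is in Section 17: "Medication adherence and change in eGFR will be compared between groups using similar models". The models referred to are those for the symptom and quality-of-life scores, where "we will first calculate change within individuals from enrollment to 12 months" and then "Analysis of covariance (ANCOVA) will be used to compare change between treatments, adjusted for baseline score". A patient therefore needs a 12-month value to contribute.

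Section 10 says: "Allograft loss and death will be cause for automatic withdrawal from the study". It adds: "If a patient unable to continue the study for any reason, an early termination visit is necessary to complete the study". A patient who departs from the treatment regimen is handled differently: "If deviation occurs from treatment, patient will continue study".

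The early termination visit appears neither in the Section 14 visit list nor in the schedule of events. No section defines an analysis population, a missing-data rule, a value for eGFR after graft loss, or a sensitivity analysis.

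**The concern.** Graft loss is the worst graft-function outcome, and it is the event that removes a patient from the graft-function analysis. Unless a rule is written, the model is fitted to patients whose graft was still working at 12 months. The result could then be reported as graft function by formulation when it is eGFR conditional on graft survival.

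Two things could follow. A formulation group with more failures could look equal to the other, because its failures are not counted. If the failing grafts are those that would have had the lowest eGFR, removing them raises that group's mean, and the group could look better.

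The result also bears on a numbered endpoint. The safety endpoint (Synopsis item 12, Section 3 item 10) includes laboratory safety changes, and the footnote to the schedule of events counts creatinine and eGFR among the safety labs.

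**Working it through.** **Figures in the plan.** None exists for eGFR: no mean, SD, effect size, power or graft-loss rate. The only related figure is the completer count in Section 17, which reproduces: 240 × (1 − 0.15) = 204. An equal split would give 102 per group, but the split is an assumption because treatment is not assigned.

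**What the text implies for a failed graft**
1. Graft loss leads to automatic withdrawal (Section 10).
2. The model needs change from enrollment to 12 months (Section 17), and the 12-month visit is day 365 ± 45 (Section 14).
3. A graft lost before day 320 (365 − 45) has no scheduled eGFR in the window. A loss inside the window might have one.
4. The early termination visit might yield an eGFR, but nothing says it is measured or may replace the 12-month value.
5. With no rule, the patient leaves the model by default.

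**Size, on assumed inputs.** None of these comes from the documents: mean eGFR 50, SD 18 (mL/min/1.73 m²), baseline-to-12-month correlation 0.6, and no formulation effect other than on graft loss. Failed grafts are given 10 or 0. A baseline-adjusted ANCOVA of change was simulated with 400,000 patients per group. Entries are group A minus group B, where A loses more grafts. Ranges cover the runs for the two assigned values. The surviving-graft estimates do not use that value, so their spread is simulation noise.

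| Loss, A v B | Loss unrelated to eGFR: surviving grafts | Same, failures counted | Lowest-eGFR grafts fail: surviving grafts | Same, failures counted |
|---|---|---|---|---|
| 2% v 2% | −0.04 to 0.01 | −0.05 to 0.03 | −0.03 to 0.00 | −0.04 to 0.00 |
| 4% v 2% | 0.00 to 0.02 | −0.78 to −1.01 | +0.41 to +0.49 | −0.11 to −0.39 |
| 5% v 2% | −0.03 to 0.05 | −1.23 to −1.44 | +0.69 to +0.71 | −0.23 to −0.54 |
| 6% v 3% | −0.03 to 0.01 | −1.20 to −1.53 | +0.72 | −0.25 to −0.57 |
| 8% v 3% | −0.04 to 0.01 | −2.00 to −2.54 | +1.11 to +1.12 | −0.57 to −1.06 |

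**Hand check.** When loss is unrelated to eGFR, counting failures at value v should shift the difference by −(loss in A − loss in B) × (50 − v).
- 4% v 2%: −0.02 × 50 = −1.0 for v = 0, and −0.02 × 40 = −0.8 for v = 10.
- 8% v 3%: −0.05 × 50 = −2.5, and −0.05 × 40 = −2.0.

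These agree with the table.

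**Gap between the two analyses**
- Smallest: 4% v 2%, lowest-eGFR grafts fail, v = 10: 0.49 − (−0.11) = 0.60.
- Largest: 8% v 3%, loss unrelated to eGFR, v = 0: −0.04 − (−2.54) = 2.50.

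**Against sampling error.** With 102 per group, the baseline-adjusted SE on these inputs is 18 × √(1 − 0.6²) × √(2/102) = 14.4 × 0.140 = 2.02. The largest surviving-graft bias, 1.1, is about 0.54 SE (1.1/2.02). The gap of 0.6 to 2.5 is about 0.3 to 1.2 SE.

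**The case against.** **The early termination visit.** A reader might infer that every patient with a failed graft certainly drops out of the model. The documents do not go that far, because Section 10 requires a closing visit and a loss within 45 days of day 365 could have a value. What stands is that the handling is undefined and that exclusion is the default.

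**Safety reporting.** A reader might infer that graft loss and death would go unseen. They would not. Section 16 tabulates SAEs by formulation. Under Section 19 death is a seriousness criterion, and graft loss would probably qualify through hospitalization or as an important medical event. The schedule also collects graft-function data from medical records. But graft loss has no line of its own, and an SAE table does not correct the eGFR estimate.

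**Direction.** A reader might infer that the planned model always favours the worse group. It does so only if the failing grafts would have had the lowest eGFR. If loss is unrelated to eGFR, the surviving-graft difference is about zero: the deficit is hidden, not reversed.

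**Size.** Multiplying a difference in loss rates by a mean eGFR can give larger figures. With an assumed mean of 55 and losses of 8% v 2%, it gives 0.06 × 55 = 3.3 units. That measures the change in what is being estimated when failures are scored 0, not the bias of the planned model. Nothing in the documents supports a fourfold difference in loss.

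**Importance.** Change in eGFR is not named as an endpoint in its own right, has no power claim, and sits in an observational pilot about symptoms. Because care teams choose the treatment, a difference in graft loss would be confounded under any analysis. All of this limits the weight of the point. It does not remove it, since graft function is a declared comparison and eGFR is among the safety labs. Non-assigned treatment also means that equal loss rates cannot be presumed.

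**Conclusion.** The concern holds in limited form. As written, the eGFR comparison defaults to surviving grafts, and the plan neither says so nor defines how failed grafts enter. The direction is conditional: a difference in graft loss is hidden in either case, and the group with more losses is favoured only when the lowest-eGFR grafts are the ones that fail.

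The size cannot be set from the documents. On assumed loss rates of 4–8% v 2–3%, the surviving-graft difference is about 0 to 1.1 units in favour of the worse group, and counting failures moves the estimate by about 0.6 to 2.5 units. These figures rest on the assumed mean, SD, correlation and assigned values. With equal loss rates the effect vanishes.

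It would be wrong to infer that the primary CIRS result is shown to be at fault. This point concerns a supporting and safety comparison, and confounding by treatment choice remains whichever analysis is used.

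**What to change.** In Section 17:

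- Keep the planned ANCOVA but label it as an analysis of surviving grafts.
- Add one prespecified analysis in which graft loss takes the worst rank, with a rank-based test, or eGFR 0.
- State separately how death with a functioning graft, other dropout and early-termination eGFR values are handled. Scoring graft loss does not settle these, and they include patients withdrawn for starting an excluded immunosuppressant.
- State what the early termination visit collects, and list it in Section 14 and the schedule of events.
- Report counts of graft loss and death by formulation beside the eGFR result.

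The cost is SAP wording and one extra model. Both events already trigger withdrawal, so no additional patients are needed. The drawback is a skewed composite: if eGFR 0 is used, the mean difference should not stand without the rank-based test. Which of the two analyses leads is a matter of judgement, provided that each is labelled for what it estimates.

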The TRS is a multi-item questionnaire capturing 15 symptoms (from PRO-CTCAE) that have been shown to be associated with transplant and general health-related quality of life improvement. These symptoms include change in taste, constipation, diarrhea, swelling in arms or legs, palpitations, dry skin, darkening of skin, blurry vision, headache, insomnia, anxiety, sadness, discouraged, increase in appetite, and fatigue. Each symptom is based on symptom severity in the last 7 days and scaled from 0 (none) – 4 (very severe). Some symptoms also have added questions pertaining to frequency and/or interference with daily activities. The sum of the severity score ranges from 0-60. The improvement in transplant symptoms will be measured by the difference between treatment groups in the mean TRS score.

4. Improvement in health-related quality of life (HRQoL), as measured by the PROMIS-29 health profile, will be compared between groups at 12 months post-kidney transplantation. The PROMIS-29 produces scores for depression, anxiety, fatigue, pain interference, sleep disturbance, physical function, participation in social roles, and pain intensity. Physical and mental health summary scores will also be calculated.

Standardized effect sizes (mean difference / standard deviation) for differences in HRQOL (PROMIS-29) scores will be calculated to compare twice daily immediate release tacrolimus oral to Envarsus XR®.

Clinical Study Protocol [#SIMPLE]

5. Improvement in individual symptoms captured in the TRS questionnaire will be compared.

The standardized effect size (mean difference / standard deviation) on TRS score will be calculated and compared between treatments. Individual TRS items will be classified as improved, worsened, unchanged and compared between treatments.

6. Improvement in overall tolerability or patient bother due to side effects, measured by item GP5 (“I am bothered by side effects of treatment”) from the FACT-G.

Patients’ GP5 responses will be classified as improved, worsened, or unchanged and compared between treatments.

7. Improvement in mean taking adherence, defined as the percent of prescribed doses taken each day (as measured by electronic monitoring), rates between groups.

The assumption is that the mean taking adherence will 75% for the twice-daily immediate release tacrolimus and 90% for the Envarsus XR® (and standard deviations of 38% and 30%, respectively).

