8. TREATMENT ASSIGNMENT

This is an observational study, and as such, treatment will not be assigned, and there is no intervention. The treatment decision will be made by each patient's transplant care team, independent of the study.

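### Individual TRS items and GP5 are compared by an unadjusted three-category change although total scores are baseline-adjusted; this costs power and, in a non-randomised study, can mislead if a baseline imbalance regresses to the mean

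*Combined protocol and SAP*

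**What the plan says.** Section 17 treats totals and items differently. For the CIRS, TRS and PROMIS-29 scores, "Analysis of covariance (ANCOVA) will be used to compare change between treatments, adjusted for baseline score". For the individual transplant-related symptoms and the single tolerability item GP5, "within-patient change on each item will be classified as improved, worsened or unchanged and compared between treatments using chi-square tests for ordinal data", with no covariate.

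Section 3 lists both as secondary endpoints and repeats the classification: "Individual TRS items will be classified as improved, worsened, unchanged and compared between treatments". The Synopsis does the same.

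The study is not randomised. Section 8 states: "This is an observational study, and as such, treatment will not be assigned, and there is no intervention". Section 17 describes no site, propensity or other confounder adjustment for any endpoint.

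Baseline item responses are already scheduled. Section 14 and the Schedule of Events list the CIRS, TRS and GP5 surveys at Visit 1, timed as "To be collected within the first 30 days post-transplant".

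**The concern.** The TRS total is adjusted for baseline and its component items are not, so total and items can disagree for reasons unrelated to treatment.

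The sign of change also depends on where a patient starts. On a five-level item, a patient at the lowest level cannot improve and one at the highest cannot worsen. On the yes/no skin-darkening item in Appendix 2, a yes can only improve or stay and a no can only worsen or stay. Because the care team chooses the formulation, nothing protects balance at baseline.

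Two things are at stake. A test that ignores a prognostic baseline score loses power even in balanced groups. In unbalanced groups, a difference in improved and worsened percentages may reflect starting level rather than formulation, or may conceal a benefit. This touches every TRS item and GP5. It does not touch the primary CIRS score.

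**Working it through.** **The plan's own item-level figure.** Section 17 claims 80% power, two-sided 0.05, to detect 0.28 SD on individual items with 204 completers (240 × 0.85 = 204, which reproduces). The allocation ratio is not stated; I assume 1:1, so 102 per group.

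- Detectable difference for two means: (1.960 + 0.842) × √(2/102) = 2.802 × 0.140 = 0.392 SD, not 0.28.
- Power at 0.28 SD: Φ(0.28/0.140 − 1.960) = 52%. For 80%: 2 × (2.802/0.28)² = 200.2, so 201 per group.
- 0.28 appears from a one-sample formula with n = 102 (2.802/√102 = 0.277), or from ANCOVA with an unstated correlation of 0.70 (0.392 × √(1 − 0.70²) = 0.280). The item-level chi-square uses neither, and the plan shows no calculation for a three-category test.

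I therefore look at both 0.28 and 0.39 SD.

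**Simulation inputs.** From the documents: 204 completers, two-sided 0.05, five response levels. Assumed: item distribution 50/27/15/6/2% over levels 0–4 (mean 0.27 + 0.30 + 0.18 + 0.08 = 0.83), cut from a latent normal variable; latent correlation ρ between baseline and 12 months of 0.3, 0.5 or 0.7; change measured from baseline to 12 months; 3,000 runs per setting. Planned test: ordinal trend chi-square on improved/unchanged/worsened. Adjusted test: ANCOVA of the 12-month item on treatment and baseline item. A test stratified by baseline level gave nearly the same results.

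| Rejection rate, planned vs adjusted | ρ = 0.3 | ρ = 0.5 | ρ = 0.7 |
|---|---|---|---|
| Balanced, true effect 0.28 SD | 24% vs 43% | 32% vs 46% | 44% vs 57% |
| Balanced, true effect 0.39 SD | 42% vs 66% | 52% vs 73% | 69% vs 84% |
| No effect, 0.3 SD shift that regresses | 19% vs 5% | 14% vs 5% | 9% vs 5% |
| No effect, stable 0.3 SD difference | 5% vs 31% | 5% vs 22% | 5% vs 15% |

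**Size of the power loss.** At 0.39 SD the equivalent sample-size ratio is ((1.96 + z_adjusted)/(1.96 + z_planned))², where z is the normal quantile of the power. At ρ = 0.3: (2.38/1.76)² = 1.8. At ρ = 0.7: (2.96/2.45)² = 1.5. The planned test needs about 1.5 to 1.8 times the patients.

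**Source of the loss.** At ρ = 0.5 and 0.39 SD, collapsed change has 52% power, uncollapsed change 55% and the baseline-adjusted test 73%. Collapsing accounts for about 3 of 21 points.

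**Mechanism.** With a regressing 0.3 SD shift, ρ = 0.3 and no effect, 29% improve in one group and 38% in the group that started worse; 29% and 26% worsen. With a stable 0.3 SD difference, improved and worsened rise together (29% to 33% each), so the change test stays at its level while the adjusted test reads the persistent gap as a treatment difference.

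**A hidden benefit.** With a true 0.39 SD effect and the Envarsus group starting 0.3 SD lower, under regression to the mean, power is 11–36% planned against 68–84% adjusted.

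**Sensitivity.** A second item distribution (latent cut-points 0.05, 0.75, 1.35, 2.0, with 52% at zero), a baseline-stratified rank test, and a common fall of 0.5 SD added to the stable case widen the ranges to about 24–45% against 41–57% at 0.28 SD, 40–69% against 64–84% at 0.39 SD, 8–19% false positives for the planned test under regression, and 14–33% for the adjusted test under a stable difference.

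**The case against.** The strongest objection is that baseline adjustment is not free here. The documents cannot show whether a baseline imbalance would regress or persist. A stable difference, for example in comorbidity or site practice, makes the adjusted test the misleading one, with an error at least as large as the planned test shows in the opposite case. This stands. A reader might infer that the planned test necessarily manufactures false differences and that adjusting has no downside; neither follows from the documents.

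Baseline may also be on treatment: Section 4 requires that the formulation already be indicated at entry, and baseline surveys may fall up to 30 days after transplant. Adjusting for an on-treatment score can remove early effect. This stands too, although change from that same baseline shares the problem.

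A change classification does match an endpoint worded as improvement, and these are secondary endpoints in a pilot study. That limits the consequence and is a good reason to keep the classification in the report. It does not explain why the plan adjusts the TRS total and the primary CIRS score, and so accepts the same assumption there, but not the items.

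Finally, the item distribution and correlations are assumed, so the ranges matter more than any single figure.

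**Conclusion.** The point holds in a conditional form. The unexplained difference between totals and items is in the text. The power loss in balanced groups is the most secure part: roughly 13 to 24 percentage points across the scenarios tabulated above. It depends on the assumed item distribution, ρ of 0.3–0.7 and 102 per group.

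False differences, and hidden benefits, are possible rather than certain. They arise if an imbalance regresses to the mean; under a stable difference the ranking of the two tests reverses.

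Two further readings are not supported. Collapsing five levels into three is not the main fault, since it explains little of the loss. Nor does the problem reach the primary analysis, which is baseline-adjusted. A change is still worthwhile, because it extends to the items a choice the plan has already made for its totals.

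**What to change.** In Section 17, analyse each 12-month TRS item response (severity where it is asked, otherwise the frequency response) and GP5 in a proportional-odds model with treatment and the baseline response to the same item. Use logistic regression for the yes/no skin item. Keep the improved/unchanged/worsened comparison as a pre-specified sensitivity analysis, report both, and say that disagreement between them may reflect baseline imbalance. Restate the item-level power for the test actually used.

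The cost is a few sentences and no new data. The plan should state the downsides: the proportional-odds assumption; possible bias if the groups differ stably; a baseline up to 30 days after transplant that may already be on treatment; and the fact that adjusting for the baseline item alone does not remove confounding from non-random treatment choice.
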